4.2.3.2.5. Global evaluation of therapy tolerability by the patient and the physician

Global evaluation of study drug tolerability should be made by the patient and Investigator according to the following scale:

Scores	Evaluation
0	Poor
1	Satisfactory
2	Good
3	Excellent

Evaluation of the study drug tolerability by the patient and the physician (points/scores) should be specified in the eCRF at Visits 2 or 3 (where applicable).

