9.1.4 Safety parameters analysis

A descriptive part of the safety analysis will include an evaluation of incidences and two-sided CI 95% for the following parameters in every trial group:

- AEs: the incidence in total and for separate categories (according to MedDRA), for the trial and by groups;
- SAEs: the incidence in total and for separate categories (according to MedDRA), for the trial and by groups;
- Incidence of clinically significant changes of the physical examination results by visits and groups;
- Incidence of clinically significant changes of the laboratory results by visits and groups;
- Incidence of clinically significant changes of the vital signs (body temperature, BP, pulse rate, HR) by visits and groups;
- Incidence of clinically significant changes of the ECG parameters by visits and groups;
- Global tolerance evaluation during the trial by the Investigator and patient.

The Fisher's exact test will be used to compare incidences between the groups, and chi-square will be used to compare the global therapy tolerability by the Investigator and patient. The McNemar's test will be used to evaluate for the dynamic changes during the trial (before—after) for all the repeatedly evaluated incidences in every group.

In addition to the incidence, all the quantitative safety parameters will be presented in a table form (laboratory results, vital signs, ECG) by visits and groups. The difference will be evaluated using 2-way-ANOVA (group and visit numbers will serve as the relevant factors). The post-hoc criteria will be used in case of significant difference.

Safety analysis will be performed on the safety population.

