2.3 Evaluation of the study drug safety and tolerance

Safety of the trial therapy is evaluated based on the systemic parameters (systolic and diastolic blood pressure, breathing rate, heart rate, body temperature, ECG), laboratory tests results, frequency of adverse events (AEs) and serious adverse events (SAEs). AEs nature and incidence (allergic reactions, burning sensation, discomfort) at the administration site will be evaluated throughout the trial. Global evaluation of treatment tolerability will be made by the patient and the physician according to the following scale:

Scores	Evaluation
0	Poor

1	Satisfactory
2	Good
3	Excellent

Evaluation of the study drug tolerability by the patient and the physician (points/scores) should be specified in the eCRF at Visits 2 or 3 (where applicable).

3 Main provisions for analysis

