3.10 Significance level

All statistical analyses in this trial will be conducted at 95% significance level (a threshold p value for confirmation of statistical significance is below 0.05), except for the primary endpoint where a one-sided statistical criterion will be used with 95% significance level (a threshold p value is below 0.05). The two-sided statistical criteria will be used for all other parameters.

For the primary endpoint evaluation, 90% CI will be calculated for the proportions difference with further evaluation of its lower boundary limit.

4 Analysis plan

For non-inferiority confirmation, a two-sided 90% CI will be calculated for the proportion difference of the primary efficacy parameters (no pain after 3 days of therapy on Day 4 according to TSS) with further evaluation of its lower boundary limit.

A non-inferiority conclusion will be made relating to the primary parameter only which will confirm the claimed efficacy. Secondary variables (including secondary efficacy and safety parameters) will be used for the research interest. Correction for multiple comparisons is not envisaged due to the trial arms number.

Descriptive statistics will include data for all randomized patients. Descriptive statistics parameters to be calculated for the quantitative variables are listed below:

- Quantity of observations (n);
- Arithmetic mean (M);
- Standard deviation (SD);
- 95% confidence interval for the mean (95% CI);
- Minimal value (min.);
- Maximal value (max.);
- Median (Me);
- Interquartile range (IQR).

For the variables presented as qualitative and serial parameters, the absolute (n) and relative (%) incidences will be calculated for every category, as well as 95% CI (unless otherwise specified).

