4.1.4 Safety and tolerability analysis

AEs incidence will be compared between the trial arms using Pearson's chi-squared test. In case of significant changes, a relative risk will be calculated (with 95% CI).

A tolerability level for every group will be calculated based on the AEs incidence and nature (in accordance with Section 2.3 of this Plan).

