4.1.5 Analysis of laboratory and functional tests results

A between group comparison of the vital signs changes (systolic blood pressure, diastolic blood pressure, breathing rate, heart rate, body temperature) revealed at every visit (Visits 1, 2, 3) as well as laboratory results and ECG changes incidence obtained at Visit 1 and Visits 2–3 is envisaged. In addition, significance of the changes will be evaluated for all repeatedly measured parameters.

The following laboratory parameters will be reviewed:

- Hematology
 - o Hemoglobin
 - o RBC
 - o ESR
 - o WBC
 - o Neutrophils
 - Juvenile
 - Stab
 - Segmented
 - o Eosinophils
 - o Basophils
 - o Monocytes
 - o Lymphocytes
- Biochemistry
 - Total protein
 - o AST
 - o ALT
 - o Total bilirubin

ANOVA methods will be used to reveal a simultaneous influence of a group and time factors on the quantitative parameters.

The cross tables analysis will be used to reveal a correlation between the qualitative parameters (chi-squared test).

For the quantitative parameters, a comparison will be made by Student's t-test for the independent samples (in case of confirmation of hypothesis on normal variables distribution) or Mann–Whitney test (in case of rejection of hypothesis on normal

variables distribution); for the qualitative parameters—using Fisher's exact test.

To evaluate significance of the intragroup changes during the trial for repeatedly measured parameters, the paired Student's t-test (in case of confirmation of hypothesis on normal variables distribution) or paired Wilcoxon signed-rank test (in case of rejection of hypothesis on normal variables distribution) will be used; for the qualitative parameters McNemar's test will be used.

5 Presentation of statistical analysis results

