Arm	Parameter	Total protein	ALT	AST	Total bilirubin
	n				
	M				
	SD				
	95% CI				
	Min.				
	Max.				
	Me				
	IQR				
	n				

M		
SD		
95% CI		
Min.		
Max.		
Me		
IQR		
р		

Table 12.A number of patients with normal and abnormal hematology parameters (Visits 1, 2, 3)

Arm	Parameter	Hemoglobin	RBC	ESR	WBC
	Reference				
	Deviation				
	Reference				
	Deviation				

Table 13.A number of patient with normal and abnormal WBC differential results (Visits 1, 2, 3)

Arm	Parameter	Neutrophils, total	Juvenile	Stab	Segmented	Eosinophils	Basophils	Monocytes	Lymphocytes
	Reference								
	Deviation								
	Reference								
	Deviation								

Table 14. A number of patient with normal and abnormal biochemistry parameters (Visits 1, 2, 3)

Arm	Parameter	Total protein	ALT	AST	Total bilirubin
	Reference				
	Deviation				
	Reference				
	Deviation				

Table 15. Concomitant diseases

Organ, system	Arm	Number of diseases (proportion, %)
		n/N (%)

Table 16. Concomitant therapy

Drug group	Arm	Number of prescriptions (proportion, %)
		n/N (%)

	n/N (%)
	n/N (%)
	n/N (%)
	n/N (%)

Table 17. Evaluation of throat pain severity according to VAS

Arm	Parameter	Visit 1	Visit 2	Visit 3
	n			
	M			
	SD			
	95% CI			
	Min.			
	Max.			
	Me			
	IQR			
	n			
	M			
	SD			
	95% CI			
	Min.			
	Max.			
	Me			
	IQR			
	p			

Table 18. TSS scores (Visits 1, 2, 3)

Arm	Amount of scores	Sore throat	Difficulty in swallowing	Salivation	Pharyngeal mucosa hyperemia	Fever
	0	n/N (%)	n/N (%)	n/N (%)	n/N (%)	n/N (%)
	1	n/N (%)	n/N (%)	n/N (%)	n/N (%)	n/N (%)
	2	n/N (%)	n/N (%)	n/N (%)	n/N (%)	n/N (%)
	3	n/N (%)	n/N (%)	n/N (%)	n/N (%)	n/N (%)
	0	n/N (%)	n/N (%)	n/N (%)	n/N (%)	n/N (%)
	1	n/N (%)	n/N (%)	n/N (%)	n/N (%)	n/N (%)
	2	n/N (%)	n/N (%)	n/N (%)	n/N (%)	n/N (%)
	3	n/N (%)	n/N (%)	n/N (%)	n/N (%)	n/N (%)
	p	n/N (%)	n/N (%)	n/N (%)	n/N (%)	n/N (%)

Table 19. Frequency of the recovery criteria achievement (total $TSS \le 2$) by Visits 2, 3

Arm	Parameter	Visit 2	Visit 3
	Criterion is met		
	Criterion is not met		
	Criterion is met		
	Criterion is not met		

Table 20. Global evaluation of treatment tolerability (Visits 2, 3)

Arm	Parameter	Tolerability evaluation by the patient	Tolerability evaluation by the physician
	n		
	M		

SD	
95% CI	
Min.	
Max.	
Me	
IQR	
n	
M	
SD	
95% CI	
Min.	
Max.	
Me	
IQR	
р	

Table 21. Registered adverse events occurred after initiation of the trial therapy

	Mile	d AEs	Moder	ate AEs	Seven	re AEs	To	otal	Total

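### The ordered 0–3 tolerability rating gets an order-blind chi-square test in the protocol and a continuous-score table with an unattributed p-value in the SAP

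*Protocol*

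**What the plan says.** **The scale.** Protocol 4.2.3.2.5: "Global evaluation of study drug tolerability should be made by the patient and Investigator according to the following scale", namely 0 Poor, 1 Satisfactory, 2 Good, 3 Excellent. SAP 2.3 repeats it: "Global evaluation of treatment tolerability will be made by the patient and the physician according to the following scale". Both say the rating is entered at Visit 2 or Visit 3, where applicable.

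**The protocol's analysis.** Section 9.1.4 lists global tolerability among the parameters to be described by incidences with two-sided 95% CIs. On the comparison it says "chi-square will be used to compare the global therapy tolerability by the Investigator and patient".

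**The SAP's analysis.** Section 4.1.4, headed safety and tolerability, gives Pearson's chi-squared test for adverse-event incidence. Its only sentence on tolerability is "A tolerability level for every group will be calculated based on the AEs incidence and nature". Section 4.1.5, on laboratory and functional tests, says "For the quantitative parameters, a comparison will be made by Student's t-test for the independent samples" (Mann-Whitney if normality is rejected) and "for the qualitative parameters—using Fisher's exact test". Neither section names a test for the 0–3 rating.

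**The SAP's display.** Table 20 has rows for n, M, SD, 95% CI, minimum, maximum, median, IQR and p, with separate columns for patient and physician. The opening of SAP section 4, Analysis plan, sets a different rule: "For the variables presented as qualitative and serial parameters, the absolute (n) and relative (%) incidences will be calculated for every category".

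**The concern.** There are two separate faults.

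The first is the choice of test. A 2 × 4 chi-square gives the same result however the four categories are arranged. If one spray is tolerated somewhat worse across the board, the test spreads its power over three degrees of freedom, although the difference runs in one direction. A rank test uses the direction.

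The second is the match between documents. A reader of the finished Table 20 would see means, SDs and a p-value, could not rebuild the category counts, and could not tell which test gave the p. SAP 4.1.4 adds to this by deriving a tolerability level from adverse events, although SAP 2.3 defines tolerability as a rated score.

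The stake is modest. Tolerability is one of the listed safety parameters in an open-label trial whose objective mentions safety, so the analysis behind a reported p-value should be fixed before the data are seen.

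**Working it through.** **1. The texts side by side.**

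| Item | Protocol | SAP |
|---|---|---|
| Scale | ordered 0–3 (4.2.3.2.5) | ordered 0–3 (2.3) |
| Display | incidences with 95% CI (9.1.4) | M, SD, median, IQR; no counts (Table 20) |
| Test | chi-square (9.1.4) | none named; p row in Table 20 |
| General rule for categories | n, % and 95% CI (9.1) | n, % and 95% CI (section 4) |
| The other 0–3 ratings (TSS items) | Mann-Whitney on reductions (9.1.3) | Mann-Whitney on reductions (4.1.3); counts in Table 18 |

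Table 20 therefore departs from Protocol 9.1.4 and from the SAP's own display rule. Table 18 follows that rule for the TSS items. SAP section 1 says that no changes from the protocol are envisaged.

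**2. Inputs for the size of the loss.** From the documents: 140 randomized per arm and two-sided alpha 0.05 for non-primary parameters (Protocol 9.2, 9.3). Neither document gives an expected tolerability distribution or effect, so there is no figure of the plan's to reproduce. *Assumed:* comparator ratings Poor/Satisfactory/Good/Excellent of 2/10/38/50%, with the Angal S ratings shifted down by a common odds ratio (OR).

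**3. The shift, at OR 1.8.** Comparator cumulative proportions are 0.02, 0.12 and 0.50.
- Odds: 0.02/0.98 = 0.0204; 0.12/0.88 = 0.1364; 0.50/0.50 = 1.
- Times 1.8: 0.0367; 0.2455; 1.8.
- Back to proportions, odds/(1 + odds): 0.035; 0.197; 0.643.
- Differences: about 3.5/16.2/44.6/35.7%.

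**4. Simulated power, 140 per arm.** Pearson chi-square on the 2 × 4 table against the tie-corrected Mann-Whitney test. Independent runs agree to about one percentage point.

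| OR | Chi-square | Mann-Whitney |
|---|---|---|
| 1.3 | 14% | 21% |
| 1.8 | 58% | 75% |
| 2.5 | 94% | 99% |

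With 128 per arm and OR 1.8 the figures are 53% and 70%. Other assumed comparator distributions (2/8/40/50, 1/4/25/70 and 10/20/40/30%), with OR 1.5 and 2.0 and 140 per arm, give a gain of about 12 to 15 points.

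**5. Type I error.** With no difference, the expected Poor count is 140 × 0.02 = 2.8 per arm. About 94% of simulated tables have at least one expected count below 5. Chi-square still rejects in only about 4 to 5% of trials, so its level holds.

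**6. The choice of test can change how a result reads.** Take invented counts of 3/11/56/70 against 5/17/62/56, with 140 per arm. Expected counts in each arm are 4, 14, 59 and 63.

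Chi-square = 2 × (1/4 + 9/14 + 9/59 + 49/63) = 3.65 on 3 df, p = 0.30. Mann-Whitney on the same data gives p = 0.060.

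**7. Where the ranking of the tests reverses.** Suppose a minority rate the spray Poor and the proportion rating it Excellent does not move: 10/8/32/50% against 2/10/38/50%, 140 per arm. Chi-square has about 72% power and Mann-Whitney about 9%. For 8/10/34/48% the figures are about 47% and 14%.

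**The case against.** The strongest reply is that chi-square is a legitimate omnibus test for a safety rating. Local reactions such as burning or allergy, which SAP 2.3 names, could affect a few patients badly and leave the rest untouched. Step 7 shows that chi-square is then far the better test. This stands. A reader might infer from step 4 that the plan is generally less likely to detect worse tolerability of Angal S, or that changing the test costs nothing. Neither follows, because the gain depends on a fairly uniform shift and the documents say nothing about the shape to expect.

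A reader might also infer that protocol and SAP prescribe contradictory tests. They do not. Only chi-square is named for this rating, and since the SAP disclaims changes, it arguably governs the p in Table 20. The mismatch is between a named categorical test and a continuous layout whose test is not stated.

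A third tempting reading is that sparse Poor cells make chi-square unreliable. Step 5 does not support it. Nor does Table 20 discard the ordering: mean, median and IQR all respect it, and the mean also assumes equal spacing between grades. Ignoring the order is a property of the chi-square test alone.

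Finally, parts of a good analysis are already there. The visit schedule yields one end-of-treatment rating per patient who completes, and Table 20 separates patient from physician.

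**Conclusion.** The point holds as a low-severity improvement. The textual part needs no assumptions: an ordered rating, an order-blind test in the protocol, and a SAP table without category counts whose p has no stated test, against both Protocol 9.1.4 and the SAP's own display rule.

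The size of the power loss is illustrative. It is about 17 points at OR 1.8, about 7 at OR 1.3 and about 5 at OR 2.5. It rests on the assumed comparator distribution, a proportional-odds shift and 140 rated patients per arm. It reverses for a difference confined to a Poor-rating minority.

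Nothing here touches the non-inferiority conclusion. SAP section 4 ties that conclusion to the primary parameter alone and treats secondary and safety variables as being of research interest.

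**What to change.** - **Test.** In Protocol 9.1.4 and SAP 4.1.4, name the Mann-Whitney test for the rating, as already used for the TSS symptom scores. Apply it to each patient's single end-of-treatment rating (Visit 2 or Visit 3), separately for patient and physician. Stating one rating per patient matters because Table 20 is headed for both visits. At Visit 2 all Group A patients but only recovered Group B patients are rated, so a by-visit comparison would not be like with like.
- **Table 20.** Replace the continuous layout with counts and percentages in each category by arm, and name the test beside the p.
- **Covering the downside.** Mann-Whitney can miss a difference limited to a minority rating Poor. Show the proportion rated Poor in each arm with its 95% CI alongside the test.
- **SAP 4.1.4.** Reconcile the sentence that derives a tolerability level from adverse events with the rated score in SAP 2.3.

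**Cost.** One sentence in each document and one revised table shell, with no new data and no effect on sample size. Because the named test changes, the protocol's own rules on amendments (11.2) and on deviations from the statistical plan (9.6) apply. The no-changes statement in SAP section 1 would need adjusting if the change were made in the SAP alone. It should be settled before the analysis starts.

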5.2 Non-inclusion criteria

The patients who comply with at least one of the criteria listed below will not be included:

- 1. Prior tonsillectomy, tonsillotomy.
- 2. Chronic conditions of the nasopharynx or oropharynx, ulcerative oral disorders.
- 3. History of hypersensitivity or allergic reactions to any components of the study drugs or local anesthetics.
- 4. Use of analgesics during less than 12 hours before the trial start and/or impossibility to discontinue the analgesics for the trial period.

- Protocol No. TE 004 ANG LOZ
 - 5. Use of antibiotics during less than 48 hours before the trial start and/or planned use of antibiotics during the trial.
 - 6. Use of topical drugs (aerosols, gargle solutions. fast-disintegrating tablets/lozenges/pastilles) in the pharynx during less than 12 hours before the trial start and/or impossibility to discontinue topical drugs, except for the study drugs, for the trial period.
 - Use of the systemic, inhalation, or nasal glucocorticosteroids during 30 days before the trial 7. start and/or planned use of the glucocorticosteroids (except for the topical skin drugs) during the trial.
 - Impossibility to discontinue other drugs which might influence the trial results, e.g., 8. antiviral or prohibited concomitant drugs (see *Prohibited concomitant therapy* section), for the trial period.
 - Signs of a primary bacterial pharyngitis or secondary bacterial infection (including body 9. temperature increase above 37.5 °C, purulent pharyngeal pellicles, significant intoxication, leukocytosis, neutrocytosis, WBC differential's shift to the left (increase in stab neutrophils, presence of younger neutrophils), ESR more than 30 mm/h).
 - 10. Granular pharyngitis.
 - Signs of rhinitis, sinusitis, otitis, eustachitis, laryngitis, tracheitis, bronchitis (such 11. conditions require therapy which might influence the trial results).
 - 12. Phenylketonuria.
 - 13. Deficit of saccharase or isomaltase (according to anamnesis data).
 - 14. Glucose-galactose malabsorption (according to anamnesis data).
 - 15. Fructose intolerance.
 - 16. Diabetes mellitus.
 - 17. Glucose-6-phosphate dehydrogenase deficiency (according to anamnesis data).
 - 18. Hemochromatosis.
 - 19. Anemia (Hb less than 120 g/l according to hematology test).
 - 20. Hyperoxaluria.
 - 21. Urolithiasis.
 - Myasthenia. 22.
 - 23. Severe, uncontrolled, cardiovascular condition which, in the Investigator's opinion, preclude the patient from participation in the trial, namely:

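### Within-arm before-after safety tests on hematology and temperature cannot be read as drug effects, because the Visit 1 value used for entry is also the baseline

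*Protocol*

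**What the plan says.** **Within-arm tests.** Protocol 9.1.4: "The McNemar's test will be used to evaluate for the dynamic changes during the trial (before—after"), in each group and for every incidence that is assessed more than once. The laboratory and vital-sign incidences listed there are of clinically significant changes. SAP 4.1.5 goes further: "To evaluate significance of the intragroup changes during the trial for repeatedly measured parameters, the paired Student's t-test", with the paired Wilcoxon test if normality is rejected and McNemar for qualitative parameters. Protocol 9.3 and SAP 3.10 set these at two-sided 0.05.

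**Entry criteria.** Protocol 5.2 bars patients with signs of bacterial infection, listing "leukocytosis, neutrocytosis, WBC differential's shift to the left (increase in stab neutrophils, presence of younger neutrophils), ESR more than 30 mm/h", and separately "Anemia (Hb less than 120 g/l according to hematology test"). Protocol 5.1 requires an axillary temperature below 37.5 °C. The synopsis makes the Visit 1 tests the basis for inclusion, and SAP 3.8 makes Visit 1 the baseline.

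**Between-arm tests.** Protocol 9.1.4: "The Fisher's exact test will be used to compare incidences between the groups". SAP 4.1.5 plans "A between group comparison of the vital signs changes", and the same for laboratory and ECG results.

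Neither document mentions selection at entry or natural recovery, or says how a within-arm p-value is to be read.

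**The concern.** The safety goals in Protocol 3.2 are comparative, but a before-after test inside one arm has no control. It detects net change over time from any cause, and here two causes other than the drug are built into the design.

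- **Selection.** Patients enter because their Visit 1 value was on the acceptable side of a limit. Ordinary within-person variation carries some of them across it by Day 4. If the abnormal category uses the same limit, nobody starts abnormal and no opposite movement can offset them.
- **Recovery.** Patients enter within 48 hours of first signs of an acute infection. As it resolves, WBC, ESR and temperature can be expected to fall whatever the treatment.

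A p-value below 0.05 could thus be taken as drug-induced abnormality, or as reassurance, when it is neither. If it appears in one arm only, it could be mistaken for a difference between the drugs. Protocol 3.1 and 9.2 include safety in the non-inferiority aim, so such statements may be given weight in the report.

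**Working it through.** The documents give no figure for these tests, so there is none to reproduce.

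**Inputs from the documents.** 128 completers per arm (Protocol 9.2); two-sided 0.05; the entry limits above.

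**Assumptions not in the documents.** Share π of screened patients beyond a given limit, 2% to 20%; Visit 1 to Visit 2 correlation r, 0.5 to 0.9; natural recovery d, 0 or 0.25 SD. There is no drug effect throughout, and the two arms are alike.

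**Step 1: number of patients needed.** Let b be the number moving from normal to abnormal, with the reverse count fixed at 0. The exact McNemar p is 2 × 0.5^b.
- b = 5: p = 0.0625.
- b = 6: p = 0.031.

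Six of 128 is 4.7%.

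**Step 2: chance of reaching six.** With b ~ Binomial(128, q), P(b ≥ 6) is 4%, 19%, 62% and 95% for q = 2%, 3%, 5% and 8%.

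**Step 3: q produced by selection.** Take standardised Visit 1 and Visit 2 values X and Y as bivariate normal with correlation r, Y having mean −d. The limit is c = Φ⁻¹(1 − π), and q = P(Y > c | X < c). For Hb the picture is mirrored. With p = P(b ≥ 6), both arms are significant with probability p² and exactly one with probability 2p(1 − p).

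| π | r | d (SD) | q | one given arm | both arms | exactly one arm |
|---|---|---|---|---|---|---|
| 2% | 0.7 | 0 | 1.4% | 1% | <0.1% | 2% |
| 5% | 0.7 | 0 | 3.2% | 23% | 5% | 35% |
| 10% | 0.7 | 0 | 5.9% | 77% | 60% | 35% |
| 20% | 0.7 | 0 | 10.9% | >99% | 99% | 1% |
| 10% | 0.7 | 0.25 | 3.2% | 22% | 5% | 35% |

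At π = 10% and d = 0, the per-arm figure is 92.5% for r = 0.5 and 28% for r = 0.9.

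**Step 4: paired t-test, π = 10%, r = 0.7.** Here c = 1.282 and λ = φ(c)/Φ(c) = 0.1755/0.90 = 0.195.
- Mean shift from selection: (1 − r)λ = 0.3 × 0.195 = 0.058 SD.
- Var(X | X < c) = 1 − cλ − λ² = 0.712.
- SD of the change: √[(1 − 0.49) + 0.09 × 0.712] = 0.758.
- Standard error: 0.758/√128 = 0.067.
- Without recovery the standardised shift is 0.87. Significant worsening has probability P(Z > 1.96 − 0.87) = 14% per arm, so 2% in both arms.
- With 0.25 SD recovery the mean is 0.058 − 0.25 = −0.192 and the standardised shift is −2.86. Significant improvement has probability 82%; significant worsening is close to 0%.

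Selection therefore matters mainly for McNemar. Recovery is the larger confounder for the paired tests.

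**The case against.** No net change is the null hypothesis of these tests, not an assumption that the design violates, and the plan nowhere attributes a rejection to the drug. That is correct. The fault lies in planning p-values with no valid reading for these parameters and leaving them unexplained.

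The McNemar model is also cleaner than the planned variables:
- Protocol 9.1.4 counts clinically significant changes, which may be rarer than out-of-range values.
- SAP Tables 12 and 13 count deviations in either direction. Assuming 5% of patients lie beyond the opposite limit (π = 10%, r = 0.7, no recovery), simulation gives significant worsening in 38–39% of trials per arm and 15% in both.
- The limits of 30 mm/h for ESR and 120 g/l for Hb need not equal the laboratory reference limits, so two-way movement remains possible. This is the reason for saying ESR is only partly affected.

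These points reduce the size of the effect; they do not make the within-arm p-value interpretable.

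The proper between-arm comparisons are already planned, and entry selection common to both arms does not bias them. SAP section 4 treats safety variables as exploratory, and the SAP table templates provide no within-arm p-value. All of this stands and limits the consequence, but the tests remain in both texts without a caveat.

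A reader might infer that the plan will report significant worsening in both arms. The documents do not support that: the both-arms probability runs from under 0.1% to 99% in the table on undocumented inputs, and with recovery the paired tests would mostly show improvement.

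**Conclusion.** The point holds for WBC, neutrophils, stab and juvenile forms, Hb and temperature, and partly for ESR. Within-arm significance on these mixes selection at Visit 1 and natural recovery with any drug effect, and cannot be attributed to treatment. The threshold is low where the category matches the entry limit: 6 of 128 patients. How often it is crossed is not fixed by the documents. Without recovery, at r = 0.7, the per-arm chance is about 1% when 2% of screened patients are beyond the limit and 77% when 10% are. These figures rest on a bivariate normal model and a one-sided category.

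Two wider readings should be resisted. The point does not extend to total protein, AST, ALT, bilirubin or ECG, which have no numeric entry limit. Nor does it touch the non-inferiority conclusion, which SAP section 4 ties to the primary endpoint alone.

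**What to change.** In Protocol 9.1.4 and SAP 4.1.5, for the entry-screened parameters only (Hb, WBC, neutrophils, stab and juvenile forms, ESR, temperature):

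1. Replace the McNemar, paired t and Wilcoxon tests with per-arm shift counts (normal to abnormal and the reverse), without p-values.
2. Base safety inference on the between-arm comparison already planned. Report the difference in the proportion with new abnormalities with a 95% CI and, for quantitative values, the baseline-adjusted difference with a 95% CI. Adjusting for the Visit 1 value, which is already collected, improves on the plain t or Mann–Whitney comparison.
3. State that the final laboratory sample is taken one day later, on Day 5, for Group B patients not recovered at Visit 2 (Protocol 4.2.4.2 and 4.2.4.3), so recovery does not cancel exactly between arms.

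The cost is wording in two documents and the loss of within-arm p-values for these parameters. No new data are needed.
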